4.5 Primary Endpoint Analysis

4.5.1 Definition of Endpoint

The primary endpoint is the change from baseline in average AM and PM scratching score to Month 6 (Weeks 21 to 24) as measured by the Albireo ObsRO caregiver instrument. It is based on the worst scratching score (item 1) of the ObsRO AM and ObsRO PM scores (Protocol Appendix 2). The detailed derivation of baseline scores and monthly scores is provided in [Appendix 2](#). Change from baseline is calculated as the monthly score minus the baseline score.

4.5.2 Estimand

The primary objective of this study is to assess the efficacy of repeated daily doses of 120 µg/kg/day odeixibat in relieving pruritus in patients with ALGS. The estimand includes all data collected through the end of the study following an ICE due to premature discontinuation of study treatment prior to Week 24 (i.e., treatment policy strategy), while excluding data following ICEs of biliary diversion surgery or liver transplant (i.e., hypothetical strategy).

On the one hand, premature treatment discontinuation could occur due to an AE, tolerability issue, lack of efficacy, or other reasons. As stated in the guidance for industry E9(R1) Statistical Principles for Clinical Trials: Addendum: Estimands and Sensitivity Analysis in Clinical Trials, the clinical and regulatory interest of hypothetical scenarios assuming the patient could tolerate treatment or did not have an AE is limited and would usually depend on a clear understanding of why and how the intercurrent event or its consequences would be expected to be different in clinical practice than in the clinical trial. Therefore, the estimand will utilize the treatment policy strategy for premature treatment discontinuation ICEs and include all data collected after this type of ICEs. This reflects the patients' outcomes in practice if they are unable to continue receiving the investigational drug. Of note, protocol section 7.1.4 specifies that for patients who prematurely discontinue study drug treatment during the treatment period, all efforts will be made to have patients continue to complete all scheduled study visits for assessments following completion of the EOT visit.

On the other hand, only a small number of patients, if any, are expected to have biliary diversion surgery or liver transplant during the placebo-controlled portion of the trial. As biliary diversion surgery may be viewed as a "rescue" treatment for pruritus, it may be reasonable for the primary analysis of pruritus outcomes to utilize a hypothetical strategy (which assumes that the biliary diversion surgery did not occur) for this ICE. A similar strategy may be reasonable for liver

transplantation, although transplantation may be indicated for reasons other than pruritus. The proposed primary analysis method will model outcomes following biliary diversion surgery or liver transplantation informed by the patients' outcomes prior to the surgery/transplant and by the trajectories of other patients in the trial.

Although not permitted by the study protocol, a significant change in anti-pruritus medication may also be considered as an ICE as it can affect the patient's scratching score and thus introduce noise into the measure of treatment effect. However, due to large number of various anti-pruritic medications with different pharmacokinetic and pharmacodynamic properties, it would be challenging from a clinical standpoint to define significant changes in anti-pruritus medication based on duration and dose collected in concomitant medication only. Therefore, change in anti-pruritus medication will not be considered as an intercurrent event in this study and all efficacy data after change in anti-pruritus medication will be included in the analyses.

4.5.2.1 Main Analysis

The primary efficacy analysis for the primary endpoint will be performed on the FAS and will be based on a MMRM excluding data after ICEs of biliary diversion surgery or liver transplant and data collected after treatment discontinuation will be included.

The change from baseline for each 4-weeks (monthly) average AM and PM scratching score will be analyzed with the SAS PROC MIXED using a restricted maximum likelihood (REML) with baseline age stratification, baseline average AM and PM scratching score, baseline direct bilirubin, treatment group, time (in months, this is a categorical variable, i.e., 1-4 weeks, 5-8 weeks, 9-12 weeks, 13-16 weeks, 17-20 weeks, and 21-24 weeks), and treatment-by-time interaction in the model. Baseline direct bilirubin is expected to be associated with the treatment effect. Unstructured covariance matrix (UN) will be used in the analysis. If this analysis fails to converge, the following structures will be tested in this order: Toeplitz (equal variances and a separate correlation for each level of separation between the time points), AR(1) (first-order autoregressive, equal variances and exponentially decreasing correlations), compound symmetry (CS) (equal variances and equal pairwise correlations across fixed time points). The first (co)variance structure yielding convergence will be used as the primary analysis. The Kenward-Roger approximation will be used to estimate denominator degrees of freedom. The primary comparison will be the difference of the least square mean (lsmean) estimate between odevixibat and placebo at Month 6 (Weeks 21 to 24). The difference of the lsmean estimate between odevixibat and placebo at other Months will be estimated and tested. Average treatment effect between odevixibat and placebo at Month 4 to 6 will be also estimated and tested.

4.5.2.2 Sensitivity Analyses

4.5.2.2.1 Sensitivity analysis 1 – Control-based MI

To assess the robustness of the primary analysis results based on MAR assumption, a sensitivity analysis based on MI for missing average AM and PM monthly scratching scores will be conducted.

The following procedures in MI will be followed:

1. Intermediate missing values are imputed by the Markov Chain Monte Carlo (MCMC) imputation model, so only monotone missing values exist after imputation. Only imputed values within the range of 0 to 4 will be used since the rating of the questionnaire is from 0 to 4.
2. The monotone missing values are imputed chronologically by month using SAS Proc MI regression method including baseline age stratification and baseline direct bilirubin in the model. For all patients with missing average scratching score for any reason, their missing average scratching score will be imputed from all placebo patients in a visit-by-visit (i.e., Month by Month) manner, regardless of study treatment assignment. This is done by each imputed data set from step 1. Only imputed values within the range of 0 to 4 will be used.
3. After the imputation, all data are pooled and the MMRM analysis is performed on each of the 200 imputed datasets.
4. The same MMRM model as in the primary analysis is used to compare the treatment effect at Month 6 (Weeks 21 to 24). This is done by the imputation IDs from step 1.
5. The results from step 4 will be combined using Rubin's method [14].

4.5.2.2.2 *Sensitivity analysis 2 - Tipping point analysis*

A tipping-point analysis will be used to explore whether missing data could have adversely impacted findings from the analysis of change from baseline in scratching score to Month 6 (Weeks 21 to 24) regardless of treatment adherence. The goal of a tipping-point analysis is to explore how the overall results may be impacted by different assumptions about the magnitude of change from baseline in scratching score to Month 6 (Weeks 21 to 24) for those with missing Month 6 (Weeks 21 to 24) data, which are sensitivity parameters (defined for each treatment group) that are systematically varied.

The tipping-point analysis will be implemented as follows:

1. 100 imputed datasets will be created using multiple imputation (MI) based on MAR, the same steps 1-2 in section 4.5.2.2.1 will be used to impute the missing average AM and PM score except that in step 2 the imputation will be done within each treatment group.
2. At each missing visit, the baseline score will be subtracted from imputed score to obtain imputed change from baseline (CHG).
3. For each patient with a missing Month 6 (Weeks 21 to 24) value, the following steps will be performed for adjusting the imputed CHG with mean zero and add the constant for the tipping steps:
 - a. The average imputed CHG will be computed based on the 100 imputed datasets from step 2 per patient.
 - b. The average imputed CHG will be subtracted from the imputed CHG per subject per imputed dataset and this is resulting in the imputed CHG among the imputed datasets for a subject having a mean of zero at month 6.
 - c. A constant ΔO and ΔP will be added to the imputed value for the odevixibat arm and the placebo arm for each of the imputed datasets.
4. Combine imputed CHG at month 6 in step 3 and other visit in step 2 with the observed CHG to get the completed 100 datasets for analyses in step 4 and 5.

5. Results from the same MMRM model as used in the primary analysis fit to the imputed datasets will be combined using Rubin's method [14]. Treatment effect estimates, p-value and limits from the 95% confidence interval (CI) will be retained.
6. The above steps will be repeated, using different values for ΔO and ΔP .

To characterize the extent of departures from assumptions that change the interpretation of the results in terms of their statistical or clinical significance, with particular interest to identify the region in the sensitivity parameter space that leads the results to no longer be statistically significant, a map of treatment effects and p-values obtained in Step 6 above will also be presented, so as to allow assessment of the differences in posited scenarios for missing outcomes, that would lead to a change in conclusion from the study results.

4.5.2.2.3 Sensitivity analysis 3 - Worst weekly scratching score for a month

The worst weekly scratching score for baseline (14-day period) and each month (28-day period) is defined in [Appendix 2](#); please also refer to the analysis window in [Appendix 3](#).

The MMRM utilized for the main analysis for the sensitivity analysis of the primary endpoint will also be used for the change from baseline in scratching score to Month 6 (Weeks 21 to 24) based on worst weekly scratching score for a month. The baseline worst weekly scratching score will be used as the covariate instead of the baseline average AM and PM scratching score in the MMRM.

4.5.2.2.4 Sensitivity analysis 4 - Worst weekly scratching score for a month with control-based MI

The MMRM utilized for the main analysis and with control-based MI utilized for the sensitivity analysis of the primary endpoint will also be used for the change from baseline in scratching score to Month 6 (Weeks 21 to 24) based on worst weekly scratching score for a month. The baseline worst weekly scratching score will be used as the covariate instead of the baseline average AM and PM scratching score in the MMRM.

4.5.2.2.5 Sensitivity analysis 5 - Primary endpoint with different definition of baseline

The MMRM utilized for the main analysis will be used for the change from baseline in scratching score to Month 6 (Weeks 21 to 24) with the baseline score redefined as following:

The baseline scratching score for this analysis is calculated by averaging the four-baseline weekly average AM and PM scores in the 28 days preceding start of treatment for whom it is available. The baseline score will be unrounded and can only be calculated if 2 or more weekly scores can be calculated.

4.5.2.2.6 Sensitivity analysis 6 - Monthly scratching score

The MMRM utilized for the main analysis of the primary endpoint will be used for the monthly scratching score at Month 6 (week 21 to 24) to evaluate scratching at a landmark time - the end of the randomized treatment period.

4.5.2.3 *Supplementary Analyses*

- **MMRM for the PP analysis set**

The same MMRM utilized for the main analysis will also be used for the PP analysis set.

4.5.3 **Subgroup Analyses**

The following subgroup analyses will be performed by using MMRM model with baseline average AM and PM scratching score, treatment group, time and treatment-by-time interaction. The approach to selection of the covariance matrix in the model will follow the same approach as for the primary endpoint.

- Age group 1: 0 to <10 and 10 to <18 years (based on actual age)
- Age group 2: 0 to <2, 2 to <12, 12 to <18 years (based on actual age)
- Region (US, EU, and rest of the world [RoW])
- Sex
- Race (White vs. Non-White (including race as not reported))
- Ethnicity (Hispanic or Latino (including ethnicity as not reported), Not Hispanic or Latino)
- Baseline serum bile acid (\geq median and $<$ median)
- The use of UDCA (Y, N)
- The use of anti-pruritus medication (Y, N)
- Child-Pugh classification (Class A, B, C)
- Hepatic impairment classification (no impairment, mild, moderate, or severe)
- Baseline direct bilirubin (>3 and ≤ 3 mg/dL and equivalent to >51.3 and ≤ 51.3 $\mu\text{mol/L}$)
- Genetic Testing for ALGS (JAG1 vs NOTCH2)

A forest plot of the subgroup analyses will be provided for the primary endpoint. Statistical analysis will be performed only when the sample size is ≥ 5 in each treatment group. If the sample size is < 5 in either treatment group, only summary statistics will be provided; the p-value will not be reported.

4.6 **Secondary Endpoints Analysis**

4.6.1 **Definition of Key Secondary Endpoint**

The key secondary endpoint is change in serum bile acid levels from baseline to the average of Week 20 and Week 24. Baseline is defined as the average of the last 2 values prior to the first dose and the average of Week 20 and Week 24 is defined as the average of values at week 20 and week 24 (refer to [Appendix 2](#) and [Appendix 3](#) for details). Change from baseline is calculated as the serum bile acid value minus the baseline value.

4.6.2 **Estimand**

The key secondary objective of this study is to assess the impact of odevixibat on serum bile acid levels in patients with ALGS. The same estimand used for the primary endpoint is also used in assessing this objective. That is, all data collected through the end of the study following an ICE

due to premature discontinuation of study treatment prior to Week 24 (i.e., treatment policy strategy), will be included while excluding data following ICEs of biliary diversion surgery or liver transplant (i.e., hypothetical strategy).

4.6.2.1 Main Analysis

The analysis for the key secondary endpoint will be determined from a MMRM modelling change from baseline for serum bile acid at each scheduled visit, with baseline age stratification, baseline serum bile acid, treatment group, visits (Weeks 4, 8, 12, 16, 20, 24), and treatment-by-visit interaction in the model. The approach to selection of the covariance matrix in the model will follow the same approach for the primary endpoint. The primary comparison of treatment difference in change from baseline to the average of Week 20 and Week 24 will be estimated and tested; also, the difference at Week 4, Week 8, Week 12, Week 16, Week 20, and Week 24 will be estimated and tested.

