#### **7.1.4 Early Discontinuation of Treatment During the Treatment Period**

Patients who prematurely discontinue study drug treatment during the treatment period will have an EOT visit as soon as possible after the decision is made to permanently discontinue study drug, and no later than their next scheduled visit. All efforts will be made to have patients continue to complete all scheduled study visits for assessments following completion of the EOT visit, as detailed in [Table 1](#). A safety follow-up visit is not required if patients continue to complete scheduled study visits after EOT. For patients who do not continue to attend scheduled study visits after EOT, a safety follow-up visit is not required if the EOT visit occurred more than 3 weeks after the last dose of study drug.

If study drug is permanently discontinued for any reason, the patient will be monitored weekly until the laboratory and clinical parameters have normalized/stabilized as clinically indicated. See [Section 10.1.3](#) regarding monitoring AEs and serious AEs (SAEs) after the patient's last study visit.

Permanent discontinuation of study drug may occur for any of the following reasons:

- Death
- Patient/caregiver estimation of intolerable symptoms
- Safety, behavior, or noncompliance with study procedures as determined by the investigator or Sponsor
- Treatment un-blinding
- An investigator's opinion that continuing the patient in the study is not appropriate. The investigator may permanently discontinue study drug at any time, if it is considered to be in the patient's best interest

If a patient permanently discontinues study drug and also withdraws consent or assent, no further assessments will be performed. Albireo may retain and continue to use any data and samples collected before such withdrawal of consent or assent.

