Key secondary efficacy endpoint: (Estimand)	Change in serum bile acid levels from baseline to the average of Week 20 and Week 24	FAS	The difference between treatment with odeixibat and placebo in mean change in serum bile acid levels from baseline to the average of Week 20 and Week 24	Premature discontinuation of study drug treatment prior to Week 24	Treatment Policy	
at Month 6 (Weeks 21 to 24) adjusting for baseline scratching in the analysis. (section 4.5.2.2.6) Supplementary analysis: The same MMRM utilized for the main analysis will also be used for the PP analysis set (section 4.5.2.3)
 
Main analysis (PRIMARY ANALYSIS): The MMRM utilized for the primary efficacy endpoint will also be used for assessment of the key secondary endpoint (section 4.6.2.1) Sensitivity analysis 1: MMRM with control-based MI (section 4.6.2.2.1) Sensitivity analysis 2: Tipping point analysis (section 4.6.2.2.2) Supplementary analysis 1: Rank transform analysis of covariance (ANCOVA) (section 4.6.2.3.1) Supplementary analysis 2: The same MMRM utilized for the main analysis will also be used for the PP analysis set (section 4.6.2.3.2)

				Undergoes biliary diversion surgery liver transplant	Hypothetical	

2 Sample Size Determination

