2.1 Sample Size and Power

Forty-five (45) patients <18 years of age were randomized at an experimental-to-control allocation of 2 to 1 in order to obtain approximately 36 completers, assuming an approximate drop-out rate of 20%. At a 1-sided significance level of $\alpha_{1\text{-sided}} = 0.025$, assuming a pooled standard deviation (SD) of 1.0, and a difference between the treatment groups of 1.2 in mean change in pruritus score from baseline to Month 6 favoring the experimental arm, the power of the study is 0.909, using the exact method (Proc Power, SAS v.9.4, Cary, NC). The key secondary endpoint is also powered for a standardized treatment effect (treatment effect/SD) of 1.2.

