4.7 Multiplicity Adjustment for Primary and Key Secondary Endpoints

Statistical testing for the primary analysis of the primary endpoint will be performed with a 1-sided Type I error rate of 0.025. The key secondary efficacy endpoint will be assessed for statistical significance if and only if the success criterion for the primary endpoint is met. This hierarchical testing strategy prevents alpha inflation from the assessment of multiple endpoints. Other secondary efficacy endpoints will provide supportive efficacy information regarding the differences between treatment with odevixibat and placebo. No alpha adjustments will be performed for multiple comparisons when testing other secondary efficacy endpoints.

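### The Week 24 window in SAP Tables 10.1 to 10.3 can drop off-treatment values that the serum bile acid estimand includes; separately, that endpoint's covariates are stated in two ways

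*SAP*

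**What the plan says.** **Estimand.** SAP 4.6.2 applies treatment policy to early stopping of study drug. For that event it includes "all data collected through the end of the study following an ICE"; only data after biliary diversion or liver transplant are left out. The endpoint averages the values that the analysis windows assign to Week 20 and Week 24 (SAP Appendix 2, Table 9).

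**Window.** In SAP Appendix 3, Table 10.1, Week 24 runs from Day 155 to the EOS date for patients who roll over into A4250-015. For those who do not, it ends one day before EOS, and the EOS date is labelled follow-up. EOS is defined only as the date of the EOS assessment. Table 10.2 (from Day 127; PedsQL, GIC/GIS, xanthoma and selected laboratory tests) and Table 10.3 (from Day 71; ultrasound, elastography, AFP) follow the same rule.

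**Visits.** Protocol 7.1.4 asks patients who stop drug early to go on attending, and adds: "A safety follow-up visit is not required if patients continue to complete scheduled study visits after EOT".

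**Model.** SAP Table 3 states: "The MMRM utilized for the primary efficacy endpoint will also be used for assessment of the key secondary endpoint". The protocol synopsis says the same. The primary model (SAP 4.5.2.1) contains baseline direct bilirubin. SAP 4.6.2.1 lists the terms as "with baseline age stratification, baseline serum bile acid, treatment group, visits (Weeks 4, 8, 12, 16, 20, 24), and treatment-by-visit interaction in the model", without it. SAP Table 8, which records changes to the protocol-planned analyses, mentions only that conjugated bilirubin became direct bilirubin.

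**Status of the test.** SAP 4.7 says "Statistical testing for the primary analysis of the primary endpoint will be performed with a 1-sided Type I error rate of 0.025" and "The key secondary efficacy endpoint will be assessed for statistical significance if and only if the success criterion for the primary endpoint is met".

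**The concern.** The values at risk in the window rule are those of patients who stopped drug and stayed in the study. The treatment-policy strategy exists to use exactly these data. If the window relabels them, the MMRM estimates their Week 24 outcome under missing-at-random, partly from patients still on drug. The analysis then no longer targets the stated estimand.

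On the model, serum bile acid is the only endpoint besides the primary that is tested under alpha control. Two covariate lists, with no rule on which prevails, leave a choice that could be made after unblinding.

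**Working it through.** **1. The plan's own figure.** SAP 2.1 says "The key secondary endpoint is also powered for a standardized treatment effect (treatment effect/SD) of 1.2"; the primary calculation gets the same ratio by "assuming a pooled standard deviation (SD) of 1.0" and a difference of 1.2. With 36 completers at 2:1 (24 and 12), 34 degrees of freedom and 1-sided alpha 0.025, the standard error is √(1/24 + 1/12) = 0.354 SD and the noncentrality is 1.2/0.354 = 3.39. Exact t-test power is 0.9094, against 0.909 stated. The figure reproduces, and neither part of this point changes it. The 0.354 SD serves below as a yardstick.

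**2. Table 10.1 applied to the patient paths the protocol allows** (Week 24 visit on Day 168 ± 3).

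| Path | Week 24 sample | EOS | Label given |
|---|---|---|---|
| Completes, rolls over | Day 168 | Day 168 | Week 24 |
| Completes, no rollover, safety follow-up held | Day 168 | Day 196 | Week 24 |
| Stops early, attends to Week 24, rolls over | Day 168 | Day 168 | Week 24 |
| Stops early, attends to Week 24, no rollover, no later visit | Day 165, 168 or 171 | same day | Follow-up |

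Only the last path loses its Week 24 value. Its Week 20 value (Days 127 to 154) is kept.

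**3. Is Week 24 the EOS assessment in that path?** This is an inference. In its favour, rollover patients have no safety follow-up visit, yet Table 10.1 gives them an EOS date that closes Week 24. EOS therefore cannot always mean the safety follow-up visit; it reads as the last assessment. Protocol 7.2.5 gives no completion date for early stoppers who keep attending, so the documents do not settle it.

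**4. Size, with assumed inputs.** Let a fraction p of the 30 odevixibat patients (two thirds of 45) follow the last path, off drug at both visits. Take an on-drug effect of −1.2 SD, an off-drug effect of 0, no effect in placebo, equal variances and Week 20/24 correlation ρ.

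- Treatment-policy contrast at each visit: −1.2(1 − p).
- Week 24 contrast when these values are dropped and predicted from Week 20: −1.2 + 1.2ρp.
- Average of Week 20 (complete) and Week 24 (predicted): −1.2 + 0.6p(1 + ρ).
- Difference from the treatment-policy value: −0.6p(1 − ρ).

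| Affected | Treatment policy | Values dropped, ρ = 0.5 | Values dropped, ρ = 0.9 | Shift (SD) |
|---|---|---|---|---|
| 3 of 30 (p = 0.10) | −1.080 | −1.110 | −1.086 | 0.030 to 0.006 |
| 6 of 30 (p = 0.20) | −0.960 | −1.020 | −0.972 | 0.060 to 0.012 |

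The shift favours odevixibat. Against the yardstick it is 0.006/0.354 = 2% to 0.06/0.354 = 17% of a standard error. If all affected patients instead stopped between Week 20 and Week 24, their Week 20 value would be on-drug and the same algebra gives 0.6p (0.06 or 0.12 SD). That is a narrower case, since every stop must fall in the last interval.

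**5. Other endpoints.** Scratching uses Table 10.4, which has no EOS rule. PedsQL, GIC/GIS and xanthoma use Table 10.2. PedsQL is analysed by ANCOVA (SAP 4.6.4.1), so no repeated-measures model stands in for a lost Week 24 value.

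**6. The two models.** Replacing baseline scratching by baseline bile acid, and months by visits, is plainly implied when the primary model is carried over. Removing bilirubin is not. The control-based MI for serum bile acid (SAP 4.6.2.2.1) borrows the steps of SAP 4.5.2.2.1, which impute with direct bilirubin and then fit the primary model. As written, main and sensitivity analyses can differ in covariates as well as in missing-data assumption. For an assumed partial correlation r of 0 to 0.5 between bilirubin and bile acid change, including it multiplies the standard error by √(1 − r²) = 1.00 to 0.87, and power goes from 0.909 to 0.967.

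**The case against.** **Window.** The loss needs several conditions together: early stopping, attendance at Week 24, no rollover, no later follow-up visit and no other sample from Day 155 to the day before EOS. A visit that is not required may still take place. The table row carrying the EOS date is described as four weeks after last dose, which suggests that its authors had the safety follow-up visit in mind. Control-based MI and a tipping-point analysis are also planned for this endpoint. All of this stands and limits the size. It does not remove the rule, which makes no exception for these patients, and the sensitivity analyses would treat as missing a value that was collected.

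A reader might turn the 20% drop-out assumption into a count of patients at risk. The documents do not support that: the figure takes 45 randomised to 36 completers, and patients who leave the study have no Week 24 sample to relabel.

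**Model.** Table 3 is a summary that points to SAP 4.6.2.1. SAP 4.6.4.1 adds bilirubin only for itching, the rank ANCOVA for bile acid (SAP 4.6.2.3.1) omits it, and Appendix 6 says covariates are adapted to each endpoint. The MMRM sample code is redacted. Table 8 is not exhaustive: it also omits the move from baseline age to the age stratum. The model without bilirubin may well be the intended one, so adding bilirubin is not clearly the right correction.

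A reader might infer that this choice could decide significance. Nothing in the documents shows that. Either covariate set is valid under randomisation, and at the planned effect the expected test statistic is about 3.39.

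**Conclusion.** The window point holds as a rule that can give a result contrary to the stated estimand. It rests on reading Week 24 as the EOS assessment for early stoppers who attend to the end, do not roll over and have no later visit. The documents do not say how many patients that is, and it may be none. With the affected patients off drug by Week 20 and the other inputs in the working, the bias is about 0.006 to 0.06 SD in favour of odevixibat: small, but avoidable and in a known direction.

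The model point is secondary. It is a real conflict of wording on an alpha-controlled test, undeclared in Table 8. Which model was meant cannot be settled from the text, and no effect on the conclusion can be claimed.

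**What to change.** - **Window.** In SAP Tables 10.1 to 10.3, for patients who do not roll over, end the Week 24 window the day before the Safety Follow-up visit only when a separate such visit took place. Otherwise run it from Day 155 (Table 10.1), 127 (Table 10.2) or 71 (Table 10.3) to EOS inclusive. State what EOS means for early stoppers who keep attending.
- **Model.** Before unblinding, fix one covariate list for serum bile acid and use it in Table 3, SAP 4.6.2.1 and the control-based MI model (SAP 4.6.2.2.1). Either keep baseline direct bilirubin, as the protocol states, or keep SAP 4.6.2.1 as it is and declare the departure in Table 8.

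The cost is SAP wording and programming, with no new data. Keeping bilirubin uses one model degree of freedom.
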